VRC 602 (NCT01993706) is titled, “*A Phase 1 Dose-Escalation Study of the Safety and Pharmacokinetics of a Human Monoclonal Antibody, VRC-HIVMAB060-00-AB (VRC01), Administered Intravenously or Subcutaneously to Healthy Adults.*”

VRC 602 was the first study of the VRC01 mAb in HIV-uninfected adults. It was a dose-escalation study to examine safety, tolerability, dose, and PK of VRC01. VRC 602 opened in December 2013 as a single site study at the NIH Clinical Center, Bethesda, Maryland and the final infusion was administered in August 2014.

As shown in [Table 4-8](#), there were 3 open-label, dose escalation groups (Groups 1, 2, and 3) for IV administration and 1 double-blinded, placebo-controlled group (Group 4) for SC administration.

Table 4-8 VRC 602 study schema

VRC 602 Groups			VRC01 Administration Schedule	
Group	Initial Enrollments	Additional Enrollments	Day 0	Week 4
1	3	2	5 mg/kg IV	5 mg/kg IV
2	3	2	20 mg/kg IV	20 mg/kg IV
3	3	2	40 mg/kg IV	40 mg/kg IV
4	SC administration			
4A	3	2	5 mg/kg SC	5 mg/kg SC
4B	3	2	Placebo SC	Placebo SC
Total		25	20 participants treated with VRC01 at different dosage levels and 5 participants treated with placebo administered SC	
IV doses administered in 100 mL of normal saline over 1 hr. First SC dose administered at about 15 mL/hr via SC infusion pump; subject option for second dose administration (Week 4) by direct SC injection with needle and syringe.				

All IV and/or SC infusions were well-tolerated with no SAEs or dose limiting toxicity.

PK analysis from VRC 602 revealed a VRC01 terminal half-life of 15 days across all IV infused dose groups. Trough levels are shown in [Table 4-9](#) below.

Table 4-9: Trough levels 28 days post first and second infusion

Time	Dose	
	20 mg/kg	40 mg/kg
28 days post infusion #1	35 mcg/ml	57 mcg/ml
28 days post infusion #2	57 mcg/ml	89 mcg/ml

4.7.1.3 HVTN 104

HVTN 104, titled *A phase I clinical trial to evaluate the safety and drug levels of a human monoclonal antibody, VRC-HIVMAB060-00-AB (VRC01) administered in multiple doses intravenously and subcutaneously in different dosing schedules to healthy, HIV-uninfected adults*, is examining safety profiles and serum levels of 5 different regimens for the IV and SC administration of VRC01 ([Table 4-10](#)). IV administration is being evaluated at doses of 10, 20, 30, and 40 mg/kg; SC administration is being tested at 5 mg/kg.

Table 4-10 HVTN 104 study schema

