9.4 Infusion visits

At all infusion visits, the following procedures are performed before infusion:

- Abbreviated physical examination, including weight, vital signs, and a symptom-directed evaluation by history and/or appropriate physical exam based on participant self-reported symptoms or complaints;
- Assessment of baseline reactogenicity parameters;
- Assessment of concomitant medications (Section 9.2);
- Assessment of any new or unresolved AEs/intercurrent illnesses; and
- Urine or serum pregnancy test (for participants who were born female). Persons who are NOT of reproductive potential due to having undergone bilateral oophorectomy (verified by medical records), are not required to undergo pregnancy testing;
- Blood collection for serum trough levels and storage (not applicable at the first infusion visit in Groups 1-3, as baseline samples will be collected at enrollment).

Following completion of all procedures in the preceding list, and if results indicate that infusion may proceed, infusion is administered (Sections 8.3 and 8.4).

Immediately following infusion, the participant remains in the clinic for observation. An initial reactogenicity assessment is made at a target of 30 minutes after all IV infusions, with an acceptable range of 25-60 minutes. Before leaving

the clinic, the participant is given the postinfusion memory tool and is instructed on how to complete it. The site will make arrangements to obtain daily reports of reactogenicity events from the participant during the reactogenicity period (Section 9.10).

The following procedures will be performed at infusion visits as specified in [Appendix L](#), [Appendix M](#), [Appendix N](#), and [Appendix O](#). These procedures may be performed prior to, during, or following infusion:

- Risk reduction counseling (Section 9.7);
- Pregnancy prevention assessment (Section 9.2 and 9.8); and
- Assessment of new or unresolved social impacts (site staff will ask participant about the status of any unresolved social impacts and if s/he has experienced any new social impacts as a result of the trial participation).
- Administration of the social impact assessment questionnaire (types of impacts assessed involve personal relationships, health insurance, life insurance, educational or employment opportunities, housing, immigration, or travel);
- Administration of behavioral risk assessment questionnaire;
- Biopsy acceptability questionnaire;
- HSV 1/2 testing

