9.11 Visit windows and missed visits

Visit windows are defined in HVTN 116 Study Specific Procedures. For a visit not performed within the window period, a Missed Visit form is completed. If the missed visit is one that required safety assessments or local safety labs, HVTN

CRS staff should attempt to bring the participant in for an interim visit as soon as possible.

Procedures performed at an interim visit are usually toxicity/safety assessments (including local safety labs) and HIV testing. With the exception of HIV testing, these procedures are performed only if they were required at the missed visit or if clinically indicated. HIV testing may be performed as deemed appropriate by the study staff. If a participant missed an infusion visit or if infusions must be permanently discontinued, see Section 7.3.2 and Section 7.3.3 for resolution.

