- ^f Cervical/vaginal swabs will be collected from females for bacterial vaginosis and *Trichomonas vaginalis* at the indicated visits and when clinically indicated.
- ^g Cervical/vaginal swabs will be collected from females for yeast only if clinically indicated.
- ^h Not applicable to HIV-infected participants.
- ⁱ Blood draws required at infusion visits must be performed prior to administration of study product; however, it is not necessary to have results prior to administration, except for results of a serum pregnancy test, if indicated. Lab tests may be drawn within the 3 days prior to infusion.
- ^j Reactogenicity assessments performed daily for at least 3 days postinfusion (see Section 9.10).

Appendix M Procedures at HVTN CRS for Group 3

Visit:	01 ^a	02	03	04	05	06	07	08	09	10	11	12	13	14	15	16	17	18	19	Post	
Day:		D-14	D0	D1-15	D29-43	D56	D57-71	D84	D85-99	D99-113	D112	D127-141	D168	D169-183	D197-211	D253-267	D351-365	D442-456	D526-540		
Week:		W-2	W0	W1-2	W5-6	W8	W9-10	W12	W13-14	W15-16	W16	W19-20	W24	W25-26	W29-30	W37-38	W51-52	W64-65	W76-77		
Month:			M0			M2		M3			M4		M6								
Procedure	Scr.		Inf1					Inf2					Inf3								
Study procedures																					
Signed screening consent (if used)	X	—	—	—	—	—	—	—	—	—	—	—	—	—	—	—	—	—	—	—	
Assessment of understanding	X	—	—	—	—	—	—	—	—	—	—	—	—	—	—	—	—	—	—	—	
Signed protocol consent	X	—	—	—	—	—	—	—	—	—	—	—	—	—	—	—	—	—	—	—	
Medical history	X	—	—	—	—	—	—	—	—	—	—	—	—	—	—	—	—	—	—	—	
Complete physical exam	X	—	—	—	—	—	—	—	—	—	—	—	—	—	—	—	—	—	—	X	
Abbreviated physical exam	—	X	X	X	X	—	—	X	—	X	—	—	X	X	X	X	X	X	X	—	
Risk reduction counseling ^b	X	X	X	X	X	—	—	X	—	X	—	—	X	X	X	X	X	X	X	X	
Pregnancy prevention assessment ^c	X	X	X	X	X	—	—	X	—	X	—	—	X	X	X	X	X	X	X	X	
Behavioral risk assessment ^d	X	—	—	—	—	—	—	X	—	—	—	—	X	—	—	X	X	—	X	—	
Confirm eligibility and obtain demographics	X	—	—	—	—	—	—	—	—	—	—	—	—	—	—	—	—	—	—	—	
Randomize ^e	—	—	X	—	—	—	—	—	—	—	—	—	—	—	—	—	—	—	—	—	
Social impact assessment	—	X	X	X	X	—	—	X	—	X	—	—	X	X	X	X	X	X	X	X	
Social impact assessment questionnaire	—	—	—	—	—	—	—	X	—	—	—	—	—	—	—	X	—	—	—	X	
Acceptability questionnaire	—	—	X	—	—	—	—	—	—	—	—	—	—	—	X	—	—	X	X	—	
Concomitant medications	X	X	X	X	X	—	—	X	—	X	—	—	X	X	X	X	X	X	X	X	
Intercurrent illness/adverse experience	—	X	X	X	X	—	—	X	—	X	—	—	X	X	X	X	X	X	X	X	
HIV infection assessment ^f	—	—	—	—	—	—	—	—	—	—	—	—	—	X	—	X	X	—	X	—	
Confirm HIV test results provided to participant	—	X	—	—	—	—	—	—	—	—	—	—	—	—	X	—	X	X	—	X	

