### **ELISA for VRC01/VRC01LS Levels in Serum**

Concentration values below the limit of quantification ( $=1.0$  ug/ml) will be replaced by  $0.5$  ug/ml in all calculations. Spaghetti plots will be used to display each participant's time-concentration curves, with the treatment group geometric mean or median overlaid. The geometric mean as well as the median and inter-quartile ranges will be used to summarize the drug level at each time-point by treatment group in a summary table.

Individual-level non-compartmental pharmacokinetics (PK) analysis will be performed. Specifically, for Groups 1-3, we will compute drug accumulation based on the ratio of observed trough drug level measurements and the area under the observed time-concentration curve (AUC) for each participant, after the second, third and fourth (Groups 1 & 2 only) infusions as compared to the first. We will report the mean, median, and standard deviation (SD), in addition to the listing of individual values. AUC will be calculated based on raw (not log-transformed) data using the linear trapezoidal method. The actual visit dates will be used in these AUC calculations.

Lastly, for each participant in Groups 1-5, the terminal elimination rate and half-life will be calculated based on the log-linear portion of the time-concentration curve after the last infusion. The terminal rate (slope) will be determined by fitting a linear regression line over the log-transformed concentrations over the actual visit date (in days). The half-life is estimated as  $\log(2)$  divided by the terminal slope. The effect of participants' characteristics on various PK parameters and inter-individual variabilities of these parameters will be modeled via population compartmental pharmacokinetics analysis and reported separately.

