### 10.3. Serum VRC01/LS Levels by ELISA

#### 10.3.1. List of Tables

- Summary statistics (i.e., N, N> LLoQ, geometric mean, median, min, max and IQR) of VRC01/LS concentration by visit (number and label), and treatment arm in all participants
- Summary statistics (i.e., N, N> LLoQ, geometric mean, median, min, max and IQR) of VRC01/LS concentration by visit (number and label), and treatment arm among participants who received all infusions
- Summary statistics (N, median and mean +/- SD) of the estimated half-life by treatment group among all participants.
- For Groups 1-3, summary statistics (N, geometric mean, median) of second vs. first, third/first, fourth vs first (if applicable) accumulation in terms of observed trough and observed AUC by treatment group among participants who received all infusions.

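### Individual serum AUC accumulation ratios rest on intervals with no early post-infusion draw, so the linear trapezoid makes them depend on draw day and biases the third/first ratio downward

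*SAP*

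**What the plan says.** SAP 8.5.2 (serum ELISA) defines accumulation in Groups 1-3 from the "ratio of observed trough drug level measurements and the area under the observed time-concentration curve (AUC) for each participant", comparing later infusions with the first. On the AUC it states "AUC will be calculated based on raw (not log-transformed) data using the linear trapezoidal method", and "The actual visit dates will be used in these AUC calculations". It asks for mean, median and SD plus a listing of individual values. SAP 10.3.1 tabulates "accumulation in terms of observed trough and observed AUC by treatment group among participants who received all infusions". The SAP does not state the concentration at time zero, the integration limits, or whether the D-14 sample serves as the pre-dose point for infusion 1.

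On sampling, Protocol Appendix L (footnote i) says "Blood draws required at infusion visits must be performed prior to administration of study product". Protocol 9.4 makes the pre-infusion trough draw "not applicable at the first infusion visit in Groups 1-3, as baseline samples will be collected at enrollment". Appendix H accordingly shows no blood at D0.

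**The concern.** The curve jumps at infusion and then falls. The plan samples before the jump and again one to 15 days later, or 15 to 29 days later in some intervals. A straight line from the pre-infusion value to a point already in decline cuts off the peak, and cuts off more the later the draw. Straight lines across gaps of four weeks or more then overstate a falling exponential. Using actual dates places the points correctly but repairs neither error.

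Two participants with identical kinetics can therefore receive different AUCs because they attended on different days. The listing and SD that the SAP asks for would show that scatter as if it were variation between people. Where one interval is sampled more sparsely than the interval it is compared with, the group summary shifts as well.

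**Working it through.** The documents give no AUC or accumulation figure to reproduce, so the check applies the SAP's rule to a known curve.

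**Inputs**
- Groups 1-2 draws (Protocol Appendices H and L): D-14; D1-15, D29-43 and D56 pre-dose; D57-71, D85-99 and D112 pre-dose; then only D127-141 (15-29 days after infusion 3) and D168 pre-dose. After infusion 4 the draws are D169-183, D197-211 and D253-267, so none falls at 56 days.
- Group 3 draws (Appendices I and M): D1-15, D29-43 and D84 pre-dose; then only D99-113 (15-29 days after infusion 2) and D168 pre-dose.
- VRC01 half-life: "PK analysis from VRC 602 revealed a VRC01 terminal half-life of 15 days across all IV infused dose groups" (Protocol 4.7.1.2). A range of 10-20 days is my assumption.
- VRC01LS half-life: no human value is given. The macaque multiples of 2.5 and 3 applied to 15 days give 37.5 and 45 days (assumption).
- Windows: "Visit windows are defined in HVTN 116 Study Specific Procedures" (Protocol 9.11). Treating the printed day ranges as windows is an assumption.

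**1. True AUC.** C(t) = exp(-kt), k = ln2/15 = 0.0462. Over 56 days, AUC = (1 - 0.0752)/0.0462 = 20.01.

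**2. SAP rule, first interval, pre-dose value 0 at time 0**
- Days 1/29: ½·1·0.9548 + ½·28·(0.9548 + 0.2618) + ½·27·(0.2618 + 0.0752) = 22.06 (+10%)
- Days 8/36: ½·8·0.6910 + ½·28·(0.6910 + 0.1895) + ½·20·(0.1895 + 0.0752) = 17.74 (-11%)
- Days 15/43: ½·15·0.5 + ½·28·(0.5 + 0.1371) + ½·13·(0.1371 + 0.0752) = 14.05 (-30%)

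22.06/14.05 = 1.57, a 57% difference from one curve.

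| Variation | Ratio of AUCs |
|---|---|
| Half-life 10 days | 17.49/8.78 = 1.99 |
| Half-life 20 days | 26.01/18.34 = 1.42 |
| VRC01LS, 84 days, half-life 37.5 days | 44.34/36.22 = 1.22 |
| VRC01LS, 84 days, half-life 45 days | 48.37/40.48 = 1.20 |
| 15 days, draws 4/32 v 12/40 | 20.13/15.55 = 1.29 |

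**3. Source of the error.** Linear interpolation alone overstates a 28-day gap by 14%. Keeping the straight rise but using a log trapezoid on the decline gives 19.5 v 12.9, a ratio of 1.51. Changing the rule on the decline therefore reduces 57% only to 51%. The rest comes from the missing early draw.

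**4. Time zero.** If the D-14 sample were entered at its own date, the first-interval AUCs would become 28.74 (days 1/29) and 17.55 (days 15/43).

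**5. Second/first ratio, Groups 1-2.** True value: 1 + 0.0752 = 1.075, for AUC and trough alike.
- Same relative draw days in both intervals: 1.08 to 1.12.
- Opposite extremes: 0.71 to 1.69.
- Draw days uniform and independent between intervals, no noise: 95% range 0.73-1.63, median about 1.10.

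**6. Third/first ratio, Groups 1-2.** True value: 1 + 0.0752 + 0.0057 = 1.081. With the single draw at mid-range (day 22), the third AUC is ½·22·(0.0808 + 0.3911) + ½·34·(0.3911 + 0.0813) = 13.22. Against 17.74 that is 0.745, and simulated medians are also close to 0.74-0.75.

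**7. Second/first ratio, Group 3, mid-range days.** 1.10 against a true 1.21 (37.5 days); 1.17 against 1.27 (45 days).

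**8. Back-extrapolation with log trapezoid, second/first ratio**
- One compartment, no noise: each interval's AUC is recovered on every draw day. This is expected, because the model matches the curve.
- One compartment, 20% noise per concentration: SD 0.24, against 0.35 for the linear rule.
- Assumed early phase (1.5-day half-life, 60% of peak), no noise: SD 0.16, against 0.46.
- Early phase of 40% to 60% of peak, no noise: 95% range from 0.91-1.26 to 0.77-1.47.

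**The case against.** A reader might infer that the accumulation ratios as a whole mostly reflect draw day. The documents do not support that. The SAP plans trough ratios as well, and these do not use the day 1-15 draw. The median second/first AUC ratio is barely biased, and 10.3.1 lists the geometric mean and median. Draw day explains 94-98% of the variance of the log ratio only when assay noise is left out; with 20% noise per concentration it explains 54%. If each participant's paired draws fall within 3 days of each other, the noise-free 5th-95th percentile range narrows to 0.98-1.22. These limits stand.

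A reader might also take the linear rule to be the whole fault, or 57% to be a general figure. Step 3 shows that the rule on the decline is a lesser cause. The 57% depends on one half-life and on the two ends of a range that the documents do not confirm as the visit window.

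The SAP also leaves inter-individual variability to a separate population PK analysis, specifies no test on the accumulation ratios, and warns that small groups limit inference (8.5.1). That lowers the stakes. It does not remove the problem, because 8.5.2 still asks for the SD and individual values, and the third/first bias reaches the group summary.

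**Conclusion.** The concern holds for the AUC accumulation ratios, not for the trough ratios. Under one compartment, a 15-day half-life and the printed ranges as windows, one VRC01 curve yields AUCs 57% apart (about 99% at 10 days, 42% at 20 days; about 20-22% for VRC01LS at 37.5-45 days). Individual second/first ratios spread over 0.73-1.63 by scheduling alone, so their SD and listing are unreliable while the median is usable. The third/first ratio in Groups 1-2, at about 0.74 instead of 1.08, would suggest falling exposure where there is slight accumulation. That is the more serious error, because a larger sample does not remove it. The arithmetic is firm. The size in practice depends on the actual visit windows and kinetics. The change should be made, but no primary endpoint fails without it.

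**What to change.** In SAP 8.5.2, replace the linear rule for accumulation AUCs, and state the time-zero value and a fixed integration interval (56 days in Groups 1-2, 84 days in Group 3). Then use one of the following:

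- Back-extrapolate the post-infusion concentration log-linearly from the first two post-infusion points, and apply the log trapezoid to the decline. After infusion 4, interpolate log-linearly to day 56.
- Take individual AUCs over the same interval from the population PK model already planned. This is preferable for the intervals with one post-infusion draw before the trough (infusion 3 in Groups 1-2, infusion 2 in Group 3).

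Report the AUC ratios from that method beside the trough ratios, and describe them as partly modelled.

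The cost is a SAP paragraph and a few lines of code, with no new samples. The downside is some dependence on the model. If there is an early distribution phase, back-extrapolation keeps part of the draw-day dependence, as step 8 shows, though it did better than the linear rule in every scenario run.

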## **8.6. Analyses prior to end of scheduled follow-up visits**

Any analyses conducted prior to the end of the scheduled follow-up visits should not compromise the integrity of the trial in terms of participant retention or safety, drug level or functional endpoint assessments.

### **8.6.1. Safety**

During the course of the trial, analyses of safety data will be prepared approximately every 4 months, as defined in Section 3 of the protocol, for review by the SMB. Ad hoc safety reports may also be prepared for SMB review at the request of the HVTN 116 PSRT. The HVTN leadership must approve any other requests for safety data prior to the end of the scheduled follow-up visits.

### **8.6.2. Anti-VRC01, anti-VRC0LS and other laboratory assessments**

Generally, analysis of a primary laboratory endpoint may be performed when all participants have completed the corresponding visit and data are available for analysis from at least 80% of these participants. The Laboratory Program will review the analysis report prior to distribution to the protocol chairs, DAIDS, vaccine developer, and other key HVTN members and investigators. Distribution of reports will be limited to those with a need to know for the purpose of informing future trial-related decisions.

## 9. SAFETY TABLES AND FIGURES

### 9.1 List of Tables

- Enrollment Report
- Demographics and Study Product Administration Frequencies
- Overall Protocol Status
- Maximum Local and Systemic Reactogenicity Summaries
- Adverse Experiences by Body System and Severity – By Decreasing Frequency
- Adverse Experiences by Preferred Term and Severity – By Decreasing Frequency – Includes Severe, Life-threatening or Fatal Events Only
- Adverse Experiences by Preferred Term and Severity – By Decreasing Frequency – Includes Events of All Severities
- Adverse Experiences by Preferred Term and Relationship to Study Product – By Decreasing Frequency – Includes Related Events Only
- Adverse Experiences by Preferred Term and Relationship to Study Product – By Decreasing Frequency – Includes Events of Any Relationship
- Adverse Experiences by Preferred Term and Relationship to Mucosal Sampling – By Decreasing Frequency – Includes Related Events Only
- Adverse Experiences by Preferred Term and Relationship to Mucosal Sampling – By Decreasing Frequency – Includes Events of Any Relationship
- Expedited Adverse Experiences (EAEs) Reported to the Regulatory Support Center (RSC)
- Pregnancy Listing
- Social Impact Summary
- End of Study Diagnostic ELISA Testing Results
- Local Lab Value Summary Statistics

### 9.2 List of Graphs

- Maximum Local Reactogenicities
  - Maximum Systemic Reactogenicities
- Boxplots for Alkaline Phosphatase, AST, ALT, Creatinine, WBC, Hemoglobin, Platelets, Lymphocyte Count, Neutrophil Count

## 10. ASSAY SPECIFIC TABLES AND FIGURES FOR PROTOCOL TEAM REPORTS

### 10.1. Viral Infectivity (TLA)

### 10.1.1. List of Tables

- Summary statistics (i.e., min, mean, median, max, standard deviation) of  $AUC_{\text{day3-21}}$  by lab, sex at birth, tissue type, virus, visit, and treatment arm.
- Results of overall comparisons of  $AUC_{\text{day3-21}}$  at baseline between FH and CHIL lab using Van Elteren test, stratified by sex at birth, tissue type and virus combination.
- Results of overall comparisons of  $AUC_{\text{day3-21}}$  at baseline between female and male rectal samples using Van Elteren test, stratified by site and virus combination.
- Results of comparisons and correlations of  $AUC_{\text{day3-21}}$  at baseline between female cervical, vaginal and rectal samples, by lab and virus.
- Results of comparisons of  $AUC_{\text{day3-21}}$  between baseline and post-infusion visits, by tissue type, virus, and treatment arm
- Results of comparisons between treatment arms at baseline based on  $AUC_{\text{day3-21}}$  and at post-baseline visits based on baseline-subtracted or unsubtracted  $AUC_{\text{day3-21}}$ , by sex at birth, tissue type, virus, and visit.
- Results of comparisons between tissue types at baseline based on  $AUC_{\text{day3-21}}$  and at post-baseline visits based on baseline-subtracted or unsubtracted  $AUC_{\text{day3-21}}$ .

